
plan
	
use.
 
(2) General investigation: dietary investigation, digestive tract symptoms, height, weight.
 
(3) Nutritional assessment: NRS2002 and PG-SGA scores, grip strength, body composition, grip strength, deltoid skin fold thickness, upper arm muscle circumference.
 
(4) Examination and examination: blood routine, biochemical set, IL-6, TNF-α, lactic acid, serum insulin, prealbumin, transferrin, chest, and abdominal CT, PETCT, etc.
 
(5) Functional Assessment of Anorexia/Cachexia Therapy (FAACT);
 
(6) QoL Evaluation Scale: ADL scale.
 
After informed consent, patients were divided into groups A and B according to their wishes.
 
Group A: According to the national industry health standard "Dietary Guidance for Patients with Malignant Tumors 2017", basic nutrition treatment, energy 30 ~ 35kcal/kg, protein 1.0-2.0g/kg, diet deficiency, total nutrition and/or whey protein oral nutrition supplement or tube feeding enteral nutrition.
 
Group B: Since basic nutrition in group A, creatine 5g/d and curcumin 4g/d were added orally for one month.
 
2. follow-up
 
Weekly telephone follow-up, 2 weeks of routine outpatient follow-up, general condition survey, nutritional intake, nutritional assessment, routine examination, anorexia/fluid therapy functional assessment, QoL rating scale, 4 weeks of effectiveness evaluation, 3 months of survival survey.

Evaluation of curative effect
	
Efficacy evaluation indicators (primary efficacy indicators and secondary efficacy indicators)
 
Main research Indicators
 
(1) Nutritional serum indexes: blood routine, biochemical complete set, prealbumin, transferrin
 
(2) Body composition index: skeletal muscle index and body composition in L3 section of CT scan
 
(3) Inflammatory metabolism indicators: serum insulin, IL-6, TNF-α, lactic acid, PETCT to evaluate the metabolism
 
Secondary study indicators
 
(1) Physical measurements: body weight, grip strength, triceps skin fold thickness, upper arm circumference diameter
 
(2) Nutritional assessment: energy and protein intake, PG-SGA score
 
(3) Functional Assessment of Anorexia/Cachexia Therapy (FAACT)

	
(4) QoL evaluation scale: ADL score
 
(5) Survival time survey: 1, 3 months survival rate
 
(6) Evaluation of tumor efficacy: Compared with the baseline at the time of enrollment, tumor remission and progression were compared

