	
Safety evaluation index
 
Creatine and curcumin taken orally by the patients in this study were both food grade: creatine is a sports nutrition food at home and abroad, which can increase muscle synthesis; Curcumin is the main component of curry, often used as a food additive, there are a variety of health food sales of curcumin abroad. After large dose of creatine supplementation (more than 25g/ day), muscle stiffness, spasm and other adverse phenomena may occur; Large doses of curcumin supplementation may cause nausea and even vomiting and diarrhea, with no toxic effects below 8g daily.
 
Both creatine and curcumin have been used orally in cancer patients in domestic and foreign studies without adverse reactions reported. The creatine (5g/ day) and curcumin (4g/ day) consumed in this study belong to the safe dosage range according to the oral dosage in domestic and foreign literatures and the dosage in the product instructions, so there are generally no side effects. For safety reasons, researchers are still closely monitoring patients for possible side effects.

Method of statistics	
Statistical analysis was performed using GraphPad Prism version 18.0 (La Jolla, CA, USA). Student's t-test was used for comparison between groups, and one-way analysis of variance (ANOVA) was used for other data. All data are presented as mean \pm SEM. $p < 0.05$(*) indicates statistical significance. $p < 0.01$(**) indicates that the difference is more statistically significant.

Duration of study	
Jun 1,2023 to Dec 31,2025

1. Background

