1.1 The purpose and significance of the research

Cancer cachexia (CAC) is a common complication of various advanced malignant tumors, which seriously affects the quality of life of patients, reduces the sensitivity and tolerance of the body to treatment, and even directly reduces the survival time of patients [1, 2]. The incidence of cachexia in digestive system tumors is significantly higher than other tumors [3].

The pathogenesis of cachexia is mainly that a series of mediators produced by tumor tissues directly or indirectly promote inflammation, resulting in increased catabolism of the body and inhibition of anabolism [4]. Although nutritional therapy is the basic treatment of tumor cachexia intervention measures, a common clinical problem is that even if the body is provided with very sufficient energy and protein, the body still does not respond, unable to enter the normal anabolic process, continuous loss of skeletal muscle and weight loss cannot be avoided, and so far there is no effective drug to correct the metabolic disorder of tumor cachexia [5, 6]. The main purpose of this study is how to make nutrition play a normal role in the synthesis of cachexia, keep the skeletal muscle and body weight not lost or less lost, and reverse the development of cachexia.

To achieve this goal, inflammation should be solved first. Many studies have found that curcumin, a plant polyphenolic compound, can effectively inhibit inflammation in tumor mice. Our group's previous studies found that curcumin can prevent the lipolysis of colon cancer mice with cachexia. In terms of anabolism, previous studies have found that creatine supplementation can promote muscle synthesis in mice, improve lean body mass and muscle mass, and partially prevent fat decomposition. Some published clinical studies have also confirmed the positive effects of oral curcumin or creatine alone on patients with cachexia [7, 8], but other studies have found that although oral curcumin alone can improve internal environment such as inflammation, the effect of lean body mass increase is not ideal [9]. Based on this, we speculate that the combination of the two may play a better and more stable synergistic effect.

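### No primary endpoint is named: nine unranked main indicators and two laboratory panels are all judged at an unadjusted p < 0.05

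*Combined protocol and SAP*

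**What the plan says.** The endpoint section of the Summary (Evaluation of curative effect) opens with "Efficacy evaluation indicators (primary efficacy indicators and secondary efficacy indicators". It then lists main indicators followed by secondary ones, so the main list is the primary tier. That list has three numbered groups:

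- "Nutritional serum indexes: blood routine, biochemical complete set, prealbumin, transferrin"
- "Body composition index: skeletal muscle index and body composition in L3 section of CT scan"
- "Inflammatory metabolism indicators: serum insulin, IL-6, TNF-α, lactic acid, PETCT to evaluate the metabolism"

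None is ranked above another. The whole analysis plan is one paragraph, in the Summary (Method of statistics) and again in section 9: "Student's t-test was used for comparison between groups, and one-way analysis of variance (ANOVA) was used for other data". It sets p < 0.05 as significant, with a second label for p < 0.01, and does not separate main from secondary indicators.

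The sample-size paragraph in section 3 rests on one variable, L3 skeletal muscle index after 4 weeks, but does not call it primary.

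On timing, the Summary gives "4 weeks of effectiveness evaluation, 3 months of survival survey". Section 5(2) agrees: serum, body-composition and inflammatory indicators are reviewed at 4 weeks for the evaluation of effect, and survival, rehospitalisation and costs are surveyed at 3 months. The schedule table in section 3 also ticks most main indicators at 3 months. It marks PET-CT p.r, without explanation, at baseline and 1 month only.

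**The concern.** With several unranked main indicators and no success rule, nothing in the plan stops one indicator with p < 0.05 from being presented as the main result, or from being chosen after the data are seen. The stated aims leave room for this. Section 1.1 speaks of wanting to "keep the skeletal muscle and body weight not lost or less lost", while the formal purpose in the Summary and section 2 is inflammation, nutrient metabolism and nutritional status. A report could lead with muscle, IL-6 or prealbumin and each time claim to follow the plan.

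Two features raise the stakes. The study is open. Section 11 also schedules a statistical analysis of the early patients for September to December 2023, followed by changes to the programme, with 76 patients still to be enrolled.

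**Working it through.** **The plan's own figure.** The documents state no overall error rate. Their only related figure is the sample size: difference 20%, SD 14%, two-sided 0.05, 80% power, 68 per group. Taken on one scale, 20/14 = 1.43 SD, which needs about 9 per group by t-test, so 68 is not reproduced. The figure of 68 per group corresponds to (1.96 + 0.84) × √(2/68) = 0.48 SD. The dropout step is reproduced: 68/0.9 = 75.6, so 76 per group and 152 in total. The mismatch is a separate issue; it is used here only to set the scale for power.

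**Count.** Single indicators: prealbumin, transferrin, L3 skeletal muscle index, L3 body composition, insulin, IL-6, TNF-alpha, lactic acid, PET-CT = 9. Panels not broken into analytes: blood routine and biochemical set = 2.

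**Chance of at least one p < 0.05 in either direction, with no true effect.** For k independent tests it is 1 − 0.95^k:

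- k = 9: 1 − 0.6302 = 0.370
- k = 8 (without PET-CT, which may not be done in every patient): 1 − 0.6634 = 0.337
- k = 11 (each panel counted as just one further test): 1 − 0.5688 = 0.431

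The documents give no correlations, so a common correlation ρ between the test statistics is assumed. The chance is then 1 − ∫ φ(x) [Φ((1.96 − √ρ·x)/√(1−ρ)) − Φ((−1.96 − √ρ·x)/√(1−ρ))]^k dx, integrated numerically. For results favouring group B only, drop the second Φ term; under independence this is 1 − 0.975^k.

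| Tests | Direction | ρ = 0 | ρ = 0.5 | ρ = 0.8 | ρ = 0.9 |
|---|---|---|---|---|---|
| 8 | either | 34% | 25% | 16% | 12% |
| 9 | either | 37% | 27% | 17% | 12% |
| 11 | either | 43% | 30% | 18% | 13% |
| 9 | favouring group B | 20% | 13% | 8% | 6% |

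The single-test comparators are 5% (either direction) and 2.5% (favouring group B).

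**Power cost of adjusting.** With 68 per group and a true difference of 0.48 SD, the t-test noncentrality is 0.484 × √(68/2) = 2.82. Power is 80% at 0.05. At the first Holm step it is 50% for nine tests (0.05/9 = 0.0056) and 65% for three (0.05/3 = 0.0167).

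**The case against.** The best defence is that L3 skeletal muscle index is already the primary endpoint in effect, because the study is sized on it at a two-sided 0.05. That is a fair inference and it makes the repair easy, but the Summary gives the index the same rank as the other main indicators. Nor can the list be read as exploratory: the plan has a formal sample size, a primary tier and a significance threshold.

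Other objections succeed in limiting the point. A reader might infer any of the following, and the documents do not support them:

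- **That 37% is the chance of falsely claiming benefit.** It counts both directions and assumes independence. In favour of group B it is 20% at most for nine tests, and correlation lowers it.
- **That the evaluation time is open.** The Summary and section 5(2) both put it at 4 weeks. The schedule table adds 3-month measurements for most main indicators but does not say that efficacy is tested then. What is missing is how those values will be used.
- **That bioimpedance muscle mass is a twelfth main test.** It is not in the Summary's main list. The schedule table has no row for L3 body composition, so the bioimpedance row may stand for that item, and counting both could count it twice.
- **That L3 muscle area is a further test.** Section 5(2) uses it to derive the index, and a measurement is not a planned comparison.

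It is also fair to say that a muscle endpoint is not the only natural primary, because the formal purpose does not name muscle. The fix therefore offers two options.

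**Conclusion.** The point stands. In the text available, the plan has a primary tier of nine single indicators and two panels with no sole primary, order, adjustment or success rule. For the nine, the chance of at least one false-positive main result is 37% if independent and 12% at a correlation of 0.9. In favour of group B it runs from 20% down to 6%. Even at a correlation of 0.9, both are more than twice the single-test rate.

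These figures assume no true effect, a true 5% error for each test, and an assumed common correlation. Nine is itself a judgement: it falls to eight without PET-CT and rises once the panels are tested. The 5% per test may not hold either, because "patients were divided into groups A and B according to their wishes". Confounding could push the real error higher, and multiplicity control does not cure that.

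**What to change.** Choose one of two options; both are sound.

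1. **Single primary.** Name L3 skeletal muscle index at 4 weeks as the only primary endpoint, tested two-sided at 0.05. Make the other main indicators secondary and report them as estimates with 95% confidence intervals. If significance claims are wanted for some, list them in advance and test that list with Holm only if the primary is significant. Without that condition, overall error could reach about 10% (0.05 + 0.05).
2. **Short co-primary set.** Pre-list a few indicators at 4 weeks that reflect the formal purpose (inflammation, metabolism, nutritional status) and test them with Holm at an overall 0.05.

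Under either option, state that 3-month marker values are descriptive, and fix the choice before the September to December 2023 analysis.

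The cost is protocol and analysis-plan wording, with no new data. Under option 1, marker results lose main-result status. Under option 2, power per endpoint falls: at 0.48 SD with 68 per group, from 80% to about 65% at the first Holm step for three tests and about 50% for nine, which is why the list should be short. Confounding from grouping by patient wish needs its own remedy.

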Study Protocol and Statistical Analysis Plan

A prospective open controlled study of creatine combined with curcumin in the intervention of early cachexia in upper gastrointestinal tumors.

NCT number: 05856500

Date: May 12, 2023

Nanjing Drum Tower hospital

The Affiliated Hospital of Nanjing University Medical School

Summary

Project Name	A prospective open controlled study of creatine combined with curcumin in the intervention of early cachexia in upper gastrointestinal tumors
Purpose of the study	
(1) To investigate whether creatine combined with curcumin can improve the inflammatory state, correct the disorder of nutrient metabolism and improve the nutritional status in the early cachexia stage of upper gastrointestinal neoplasms.
 
(2) To investigate whether creatine combined with curcumin can improve the quality of life and prognosis of patients with early cachexia in upper digestive tract tumors.

Study Design	The effect of creatine combined with curcumin on inflammatory state, nutritional metabolism, nutritional state and prognosis of patients with early cachexia of upper digestive tract tumors was investigated in a prospective open controlled study
Total number of cases	152 cases
Criteria	
Inclusion Criteria:
 
(1) Clinical diagnosis of advanced tumors of the upper digestive tract with untreatable or postoperative recurrence of esophageal and gastric cancer III-IV
 
(2) Meet the diagnostic criteria of early cachexia (anorexia and metabolic changes, involuntary body mass reduction $\leq 5\%$ within 6 months)
 
(3) Radiotherapy, chemotherapy, or immunotherapy in our hospital
 
(4) Understand and fill in a variety of rating scales
 
(5) Informed consent, voluntary participation in this study
 
Exclusion Criteria:
 
(1) Neoadjuvant chemotherapy patients
 
(2) Intestinal obstruction or gastrointestinal bleeding
 
(3) Severe heart, lung and renal insufficiency
 
(4) Coagulopathy
 
(5) Clinical diagnosis with diabetes and other metabolic diseases
 
(6) The expected survival time is less than 1 month
 
(7) With cognitive dysfunction or poor coordination
 
(8) Allergy to creatine or curcumin
 
(9) With a history of drug abuse
 
(10) Doctors or researchers deem unsuitable for study participation

Treatment	
1. Patients were enrolled for baseline investigation:
 
(1) Disease status: disease stage, complications, treatment, treatment stage, drug

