It was assumed that after 4 weeks of oral administration of creatine + curcumin in group B, combined with the existing literature on the improvement of the quality of the bad fluid, the skeletal muscle index at L3 section of CT scan in group B was 20% higher than that in control group A, and the standard deviation was 14%. Bilateral test was required, α was 0.05, the sample ratio between the two groups was 1:1 (i.e., the number of cases in the two groups was equal), $\beta=0.2$. The degree of assurance (test efficacy) $1-\beta=80\%$ was calculated using SPSS software, then the sample size of each group was 68 cases, considering the 10% loss of follow-up rate, each group needed 76 cases, 152 patients in total.

Follow-up test item time point

Classification	Item	0	0.5m	1m	3m
Serological indicators	blood routine	√	-	√	√
	biochemical set	√	-	√	√
	prealbumin	√	-	√	√

	transferrin	√	-	√	√
Body composition index	CT scans skeletal muscle index at L3 cross section	√	-	√	√
	BIA measures muscle mass	√	-	√	√
Inflammatory metabolic indicators	Serum insulin	√	-	√	√
	IL-6	√	-	√	√
	TNF- α	√	-	√	√
	lactic acid	√	-	√	√
	PETCT (SUV)	p.r	-	p.r	-
Physical measurements	Weight	√	√	√	√
	grip strength	√	√	√	√
	skin fold thickness	√	√	√	√
	upper arm circumference	√	√	√	√
nutrition assessment	intake	√	√	√	√
	PG-SGA score	√	√	√	√
Questionnaire Survey	Functional Assessment of Anorexia/Cachexia Therapy(FAACT)	√	√	√	√
	ADL evaluation scale	√	√	√	√

4. Criteria

Inclusion Criteria:

(1) Clinical diagnosis of advanced tumors of the upper digestive tract with untreatable or postoperative recurrence of esophageal and gastric cancer III-IV

- (2) Meet the diagnostic criteria of early cachexia (anorexia and metabolic changes, involuntary body mass reduction $\leq 5\%$ within 6 months)
- (3) Radiotherapy, chemotherapy, or immunotherapy in our hospital
- (4) Understand and fill in a variety of rating scales
- (5) Informed consent, voluntary participation in this study

Exclusion Criteria:

- (1) Neoadjuvant chemotherapy patients
- (2) Intestinal obstruction or gastrointestinal bleeding
- (3) Severe heart, lung and renal insufficiency
- (4) Coagulopathy
- (5) Clinical diagnosis with diabetes and other metabolic diseases
- (6) The expected survival time is less than 1 month
- (7) With cognitive dysfunction or poor coordination
- (8) Allergy to creatine or curcumin
- (9) With a history of drug abuse
- (10) Doctors or researchers deem unsuitable for study participation

Removal Criteria:

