Group B control group: In addition to the above basic nutrition, oral creatine powder 5g qd, curcumin capsule 2g bid for one month.

The intake, complications and survival of the patients were followed up by telephone for 1 and 3 weeks, physical indicators, nutritional assessment, FAACT and QoL scale were followed up for 2 weeks in the hospital and outpatient department, and nutritional serum indicators, body composition indicators, inflammatory metabolism indicators, physical indicators, nutritional assessment were reviewed for 4 weeks. Evaluation of effect. The long-term survival, re-hospitalization and hospitalization expenses were investigated 3 months later. To evaluate the effect of creatine combined with curcumin on improving the nutritional status, metabolic level and clinical prognosis of alimentary tract neoplasm. Note: Weight is calculated by standard weight: Standard weight (kg) = height (cm)-105.

(3) Combination of drugs

During the study period, patients may have been treated with chemotherapy drugs and immunotherapy drugs due to tumor treatment and may have taken megestrol orally against the oxalic fluid to improve appetite. To avoid the influence of the two groups of therapeutic drugs, the diseases, and drugs of the two groups will eventually be grouped and stratified to eliminate the interference of combined drug use.

(4) Safety evaluation index

- ① Incidence and severity of side effects
- ② The rate of unplanned rehospitalization.

6. Observation of adverse events

Adverse Event (Adverse Event): An adverse medical event occurs after a patient or clinical trial subject receives a drug or a formula for a special medical use, but there is not necessarily a causal relationship.

Serious Adverse Event: An event occurs during the clinical trial that requires hospitalization, prolongates the hospital stay, causes disability, affects the ability to work, threatens life or death, or

results in congenital malformations.

Adverse reaction: an adverse reaction that is harmful rather than expected but is causally related to the application of a drug or special medical use formula food during normal application of the drug or special medical use formula food at prescribed doses. In clinical trials for a new use, all reactions that are harmful and not causally related to the use of a drug or a formula for special medical use, as expected, should be considered adverse when the dose has not been determined.

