The clinical study will develop a data safety monitoring plan according to the risk. All adverse events are recorded in detail, properly handled and tracked until properly resolved or the condition is stable, and serious adverse events and unexpected events are reported to the Ethics Committee, competent authorities, sponsors and drug regulatory authorities in a timely manner in accordance with regulations; The principal investigator conducts regular cumulative reviews of all adverse events and holds investigator meetings where necessary to assess study risks and benefits; For studies with greater than minimum risk, an independent data monitor will be assigned to monitor the study data. For high-risk studies, an independent Data Safety Monitoring committee will be established to monitor the accumulated safety and efficacy data and make recommendations on whether to proceed.

9. Statistical analysis

Statistical analysis was performed using GraphPad Prism version 8.0 (La Jolla, CA, USA). Student's t-test was used for comparison between groups, and one-way analysis of variance (ANOVA) was used for other data. All data are presented as mean \pm SEM. $p < 0.05$ (*) indicates statistical significance. $p < 0.01$ (**) indicates that the difference is more statistically significant.

10. The ethics of clinical research

Clinical research will follow the relevant regulations such as the Declaration of Helsinki of the World Medical Congress. Clinical studies are conducted only after the protocol is approved by the Ethics Committee prior to the start of the study. Before each subject is enrolled in this study, the investigator is responsible to give a complete and comprehensive introduction of the purpose, procedure and possible risks of this study to the subject or his/her agent and sign a written informed consent. Subjects should be informed that they have the right to withdraw from this study at any time, and informed consent should be kept as a clinical study document for future reference. Subjects' privacy and data confidentiality will be protected during the study.

11. Research schedule

Jun 1,2023 to Aug 31,2023: The formal implementation of the project was started. 76 cases were collected, and baseline investigation was conducted for enrolled patients. The patients were not randomly enrolled, and grouped intervention was performed.

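### The whole blood routine is a main nutritional efficacy indicator in patients on anticancer treatment, so an unadjusted group difference in white cells or platelets can reflect treatment type or timing rather than nutrition

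*Combined protocol and SAP*

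**What the plan says.** The Summary (Evaluation of curative effect, Main research Indicators, item 1) lists "Nutritional serum indexes: blood routine, biochemical complete set, prealbumin, transferrin". The blood routine appears as a whole panel, with no component singled out.

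Four other parts of the plan bear on how it can be read:

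- **Who is enrolled.** Inclusion criterion (3) in section 4 is "Radiotherapy, chemotherapy, or immunotherapy in our hospital". Section 5(3) adds that "patients may have been treated with chemotherapy drugs and immunotherapy drugs due to tumor treatment" during the study.
- **How groups are formed.** According to the Summary, "patients were divided into groups A and B according to their wishes". Section 3 confirms that grouping is non-random and open.
- **When blood is drawn.** The follow-up table in section 3 puts the blood routine at 0, 1 and 3 months. Section 5(2) says that "nutritional serum indicators, body composition indicators, inflammatory metabolism indicators, physical indicators, nutritional assessment were reviewed for 4 weeks". Neither place ties a draw to the anticancer treatment schedule.
- **How it is analysed.** Section 9 states that "Student's t-test was used for comparison between groups, and one-way analysis of variance (ANOVA) was used for other data". It names no covariate and no stratum.

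Two provisions work in the plan's favour. The baseline survey includes "Disease status: disease stage, complications, treatment, treatment stage, drug" use, and section 5(3) says that "the diseases, and drugs of the two groups will eventually be grouped and stratified to eliminate the interference of combined drug use".

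**The concern.** That cytotoxic drugs and radiotherapy can lower blood counts is general knowledge; the protocol does not discuss it. Its rationale for the supplements (sections 1.1 and 1.2.3) concerns inflammation, muscle and fat. It gives no reason to expect white cells or platelets to respond.

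Because patients choose their group, nothing in the design balances treatment modality, regimen or time since the last treatment. If these differ between groups, an unadjusted test on a count attributes the difference to creatine and curcumin. The result would then be reported as a main nutritional effect.

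**Working it through.** **1. Is there a plan figure to reproduce?** Not for blood counts: the documents give no count data, regimen mix or cycle length. The only sizing figure, 68 per group, is for the L3 skeletal muscle index (section 3). Its stated inputs (difference 20%, SD 14%, two-sided alpha 0.05, power 80%) give 2 × (1.960 + 0.842)² × (14/20)² = 7.7, so 8 per group. The 68 is therefore not reproduced, although 68/0.90 = 75.6 does round up to the stated 76. That is a separate matter. Here 68 serves only as the planned number of analysable patients per group.

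**2. What does imbalance in treatment do to an unadjusted test?** This is an illustration. Assume no supplement effect, a therapy that shifts a count by e SD, and shares on that therapy of p₁ = 0.5 + x/2 and p₂ = 0.5 − x/2.

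- Spurious mean difference: e·x
- Within-group variance: v = 1 + e²·[p₁(1 − p₁) + p₂(1 − p₂)]/2
- λ = (e·x/√v)·√(68/2)
- Rejection probability: Φ(λ − 1.96) + Φ(−λ − 1.96)

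For e = 1 and x = 0.20: v = 1 + 0.24 = 1.24, λ = (0.20/1.114) × 5.831 = 1.047, and the rejection probability is 18.2%.

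| Shift in count | No imbalance | 10 points | 20 points | 30 points |
|---|---|---|---|---|
| 0.5 SD | 5.0% | 5.9% | 8.7% | 13.6% |
| 1.0 SD | 5.0% | 8.2% | 18.2% | 35.2% |
| 1.5 SD | 5.0% | 10.8% | 29.1% | 56.9% |

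**3. What happens with no imbalance?** The error rate stays at 5%, and treatment adds only noise. At a 50:50 mix, its share of the variance in the count is 0.25e²/(1 + 0.25e²): 6%, 20% and 36% for shifts of 0.5, 1.0 and 1.5 SD. It reaches 50% only at 2 SD. For an effect that 68 per group would detect with 80% power (0.484 SD), power falls to about 78%, 71% and 62% for the first three shifts, and to 51% at 2 SD.

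**4. Do calendar draws match treatment phase?** Cycle length is an assumption here. With a baseline on a dosing day, a draw at day 28 falls 28 mod 14 = 0, 28 mod 21 = 7 or 28 mod 28 = 0 days after a dose, for 14-, 21- and 28-day cycles. Phases match for the first and third and are a week apart for the second. A mix of regimens gives a mix of phase shifts. This biases the group comparison only if regimen or phase differs between groups.

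**5. Do the existing provisions cover it?**

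| Source of confounding | Baseline survey | Section 5(3) | Section 9 |
|---|---|---|---|
| Disease and drugs | Recorded | Stratification intended; no strata or method given | Absent |
| Radiotherapy | Within treatment recorded | Not mentioned | Absent |
| Time since last treatment, at each draw | Treatment stage, at baseline only | Not mentioned | Absent |

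**The case against.** The strongest defence has four parts.

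- **The panel has a nutritional rationale.** Section 1.2.1 lists anemia, beside hypoproteinemia, among the main clinical manifestations of cachexia. This stands for haemoglobin. A reader might infer that the blood routine has no place in a nutritional assessment, but the documents do not support that. The argument does not extend to white cells or platelets.
- **The confounding is already addressed.** Section 5(3) is aimed at differences in concurrent drugs, and treatment stage is recorded at baseline. This stands in part: the intention is real, but it lacks a method, leaves out radiotherapy and cycle timing, and does not reach section 9.
- **The effect may be modest.** A reader might infer that counts at 1 month mainly measure marrow suppression. Nothing in the documents quantifies that, the three permitted modalities need not act on counts alike, and treatment would need a shift of about 2 SD to explain half the variance. Nor can it be said that a nutritional effect would be invisible without imbalance: power falls, but the test stays valid.
- **Both groups follow the same calendar.** This is correct. A within-patient phase shift is not in itself a between-group bias. It becomes one when self-chosen groups differ in regimen or timing, which the plan neither prevents nor measures at follow-up.

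**Conclusion.** The concern holds in a limited form. An undifferentiated count panel is a main nutritional outcome in patients on anticancer treatment, with self-chosen groups, calendar-based draws and unadjusted tests. A group difference in white cells or platelets can therefore reflect the type or timing of anticancer treatment.

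The size cannot be computed from the documents. Over the assumed range (shifts of 0.5 to 1.5 SD, imbalances of 10 to 30 points) the false-positive rate for a single count runs from 5.9% to 56.9%; with no imbalance it is 5%. These figures rest on assumed shifts and imbalances and on 68 analysed per group.

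The point does not touch the L3 skeletal muscle index as the sizing endpoint. It is worth acting on because the correction is nearly free.

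**What to change.** - **Main research Indicators (1).** Remove white cell and platelet counts and report them under the safety evaluation in section 5(4), which now lists side effects and unplanned rehospitalization but no laboratory measure. If a blood-count measure stays in efficacy, limit it to haemoglobin and name it.
- **Data collection.** At each blood draw, record treatment modality, regimen and days since the last anticancer treatment.
- **Section 9.** Replace the unadjusted t-test for the remaining blood-based indicators with a comparison adjusted for baseline value, modality or regimen, and days since last treatment. This also gives the stratification promised in section 5(3) a defined method.

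Days since last treatment is measured after baseline. If the supplements change how well treatment is tolerated, as section 1.1 hopes, adjusting for it could remove part of their effect, so the model should also be reported without that term. Adjustment does not cure unmeasured differences between self-chosen groups.

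Moving the 1-month draw to a nearby pre-dose visit is not a dependable alternative. With an assumed 21-day cycle and dosing on days 0, 21 and 42, day 28 is 7 days after one dose and 14 days before the next, so no pre-dose visit is close. The rule would also leave the baseline phase uncontrolled.

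Cost: part of one panel no longer counts as efficacy, one extra case-report entry is needed at each draw, and section 9 needs a few lines. No blood test is added or dropped.
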